Independent Committees/Reviewers	A Data Monitoring Committee (DMC) and Clinical Events Committee (CEC) will be established for this study 
- DMC will assess clinical safety data on regular intervals and make recommendations on study adaptations.- CEC will adjudicate primary safety endpoint events. 
Independent Core Laboratories will conduct objective evaluations of remote arrhythmia monitoring and ECG tracings for presence of atrial arrhythmia and will perform an independent analysis of collected images (Cerebral MRI, Endoscopy, CT/MRA) for evaluation of safety.

Time and Events Schedule	See Table 1 below
---------------------------------	-------------------

Table 1: Subject Treatment and Follow-up Schedule

Assessments ²²	Pre-Procedure	Pre-Discharge	Follow-up					
			7 Day	1 Month	3 Month	6 Month	12 Month	UNS
Study Day			D7	D30	D90	D180	D365	
Visit window			D7-D9	D23-D37	D76-D104	D166-D194	D335-D379	
Clinic visit	●	●	● ⁶	●	●	●	●	● ²¹
Phone call			●					
Patient Informed Consent ¹	●							
Demographics	●							
Medical History ²	●							
Pregnancy test ³	●							
LA and LVEF assessment ⁴	●							
Left atrial thrombus detection ⁵	●							
Pericardial fluid assessment		●						
12 Lead ECG ⁶	●	●		●	●	●	●	● ²¹
Atrial Arrhythmia monitoring (Remote) ⁷				●	●	●	●	● ²¹
Atrial Arrhythmia monitoring (24-hour Holter) ⁸					●	●	●	● ²¹
Repeat ablations ⁹			●	●	●	●	●	● ²¹
Concomitant Medication ¹⁰	●	●	●	●	●	●	●	● ²¹
Device Deficiencies		●						
Adverse Events ¹¹	●	●	●	●	●	●	●	● ²¹
AFEQT ¹²	●				●	●	●	
Cardiac CT/MRA ¹³	●				● ¹³			
PV Durability Subset								
3D Electro anatomical mapping ¹⁴	●				● ¹⁴			
Endoscopy Subset								
Endoscopy		● ¹⁵						
Neurological Subset								
Cerebral MRI ¹⁶	● ¹⁸	● ¹⁹		● ²⁰	● ²⁰	● ²⁰	● ²⁰	● ²¹
Neurological Exam ¹⁷	● ¹⁸	● ¹⁹		● ²⁰	● ²⁰	● ²⁰	● ²⁰	● ²¹
NIH Stroke Scale ¹²	● ¹⁸	● ¹⁹		● ²⁰	● ²⁰	● ²⁰	● ²⁰	● ²¹
mRS	● ¹⁸			●	● ²⁰	● ²⁰	● ²⁰	● ²¹
MMSE ¹²	● ¹⁸			●	● ²⁰	● ²⁰	● ²⁰	● ²¹

1. Procedure must be done within 60 days of consent.
2. Medical history-including but not limited to arrhythmia, AAD therapy failure, heart disease (NYHA), vital signs, CHA2DS2 VASc Score and thromboembolic events.
3. In all women of childbearing age and potential. To be completed within 72-hours prior to ablation procedure.

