4. Imaging within 6 months prior to procedure to assess the LA and LVEF, in case the imaging assessment is older than 6 months, LA/LVEF dimensions shall be re-measured during the index ablation procedure prior to insertion of the study catheter.
5. Performed the day before procedure or day of ablation procedure to rule out the presence of atrial thrombus using one of the following modalities TEE, ICE, CT, MRI.
6. Data from 12-lead ECG recordings will be collected (For pre-procedure, can be performed before ICF signature)
7. Arrhythmia monitoring via remote monitoring once per week as from 1-month follow-up visit to the end of 5-month follow-up and monthly as of 6-month follow-up visit and whenever subject feels symptoms.
8. Arrhythmia monitoring via 24H Holter, site to contact subject and verify if any symptoms experienced during the Holter monitoring.
9. Information on any repeat ablation after the index ablation procedure will be collected
10. Concomitant medication: only cardiac (i.e., anti-arrhythmia drugs, anticoagulation regimen) & index ablation procedure related (i.e., adenosine, anticoagulation (i.e., heparin, pain medication)

11. AEs must be collected from the time the subject signs the informed consent onward.
12. Patient questionnaires will only be used in countries with validated languages.
13. For all subjects: CT/MRA to be completed within 6 months prior to the index ablation procedure. Post procedure: for CT/MRA subset to be repeated at 3M FU, for all subjects CT/MRA to be repeated post procedure in case subject presents with PV stenosis symptoms.
14. For PV Durability subset: an electro anatomical map, activation and voltage re-map is to be performed pre and post procedure and to be repeated at 75 days post procedure (+/- 15 days).
15. For Endoscopy subset: Endoscopy preferable between 1 day to 3 days (72hours) post procedure. For procedures on Friday a window of a maximum of 96 hours is justified.
16. If observations are noted on the post-procedure MRI, the subject must have follow-up MRI at the next follow-up visit(s) until observations are resolved.
17. A certified/qualified physician expert must perform neurologic exams at pre-and post-ablation and possibly at other follow-up visits, pending previous findings of micro-emboli/neurologic deficits.
18. To be completed within 72-hours pre-procedure. For procedures on Monday a window of a maximum of 96 hours is justified.

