19.3 Analysis Sets

Safety Population Analysis Set (SP): The SP analysis set will consist of all enrolled subjects who have had insertion of the study catheter, regardless of energy delivery.

Modified Intention-To-Treat (mITT) Analysis Set: The mITT analysis set will consist of enrolled subjects who meet eligibility criteria and have had insertion of the study catheter.

Per Protocol (PP) Analysis Set: The PP analysis set will consist of subjects who satisfy the following criteria:

- Have undergone ablation using PF and/or RF energy via the investigational ablation system per CIP
- Are treated for the study-related arrhythmia
- Are enrolled and without major CIP deviation that would affect the scientific integrity of the safety and effectiveness, including but not limited to the following:
 - Subjects found not meeting eligibility criteria
 - Failure to check for entrance block for each targeted PV after adenosine/isoproterenol challenge.

- Use of the investigational ablation system outside the PV region. A CTI line for documented typical AFL identified prior to or during the procedure using investigational system or commercial RF devices to complete the procedure is allowed during index or repeat ablation procedure (within blanking). For the treatment of arrhythmia outside the PV region, using commercial RF devices to complete the procedure is allowed. However, subjects using commercial RF devices for the non-PV regions and/or CTI lines will be excluded from the 12-month effectiveness analysis.
- Missing all CIP specified electrocardiographic effectiveness monitoring

Neurological Assessment (NA) Analysis Set: The NA analysis set will include 30 subjects who have had pre-and post-index-ablation procedure MRI and neurological assessments completed. Subjects with no pre-index ablation procedure MRI assessment and no lesions observed on post-MRI assessment will be included for analysis.

Esophageal Endoscopy (EE) Analysis Set: The EE analysis set will include 30 subjects who have had a readable 1 to 3 days post index-ablation procedure esophageal endoscopy assessment.

Cardiac CT/MRA Analysis Set: The CT/MRA analysis set will include 30 subjects who have readable outcomes at baseline and 3 months.

PVI Durability Analysis Set: The PVI durability analysis set will include 30 subjects who have readable electro-anatomical mapping at index ablation procedure and 75 days (+/-15 days) post index ablation procedure.

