### 5. Analysis Sets

Analysis sets in this study are defined as the following:

- **Safety Population Analysis Set (SP):** The SP analysis set will include all enrolled subjects who have had the study catheter inserted, regardless of whether energy is delivered or not.
- **Modified Intention-To-Treat (mITT) Analysis Set:** The mITT analysis set will include enrolled subjects who meet the eligibility criteria and have had the study catheter inserted, regardless of whether energy is delivered or not.
- **Per Protocol (PP) Analysis Set:** the PP analysis set will only include enrolled eligible subjects who have undergone the ablation procedure using PF and/or RF energy via the investigational ablation system for the study-related arrhythmia. Subjects who have major protocol deviations that could affect the scientific integrity of the safety and effectiveness will be excluded from the PP analysis set, which includes (but not limited to):
  - Subjects who are found not to meet the eligibility criteria after undergoing the ablation procedure.
  - Subjects who fail in checking entrance block for each targeted PV after adenosine/isoproterenol challenge.
  - Subjects who undergo ablation using the investigational ablation system outside the PV/CTI region
  - Subjects who miss all CIP specified electrocardiographic effectiveness monitoring records.

- **Neurological Assessment (NA) Analysis Set:** The NA analysis set will include all NA subset subjects who have met the additional eligibility criteria specific for the NA subset and have had pre- and post-index-ablation procedure MRI and neurological assessments completed. Subjects who do not have a pre-index ablation procedure MRI assessment but have no lesions observed on post-procedure MRI assessment will still be included for analysis.
- **Esophageal Endoscopy (EE) Analysis Set:** The EE analysis set will include all EE subset subjects who have met the additional eligibility criteria specific for the EE subset and had a readable result of esophageal endoscopy assessment that is done within 1 to 3 days after the index-ablation procedure. Only subjects who have a readable esophageal endoscopy assessment within the specified time frame will be included in analyses for the EE endpoints.

*Note: Endoscopy preferable between 1 day to 3 days (72hours) post procedure. For procedures on Friday, a window of a maximum of 96 hours is justified.*

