### 7.12.2 Analysis of NA Endpoint

The following analyses of neurological evaluations will be conducted and summarized descriptively. The analysis will be performed in the Neurological Analysis Set.

In addition to the criteria stated below, subjects will undergo full neurological follow-up only if neurologic symptoms and/or cerebral ischemic lesions are identified in a prior evaluation; results for these additional neurological evaluations will be summarized descriptively.

- **Neurological Exam:** The incidence of new or worsening neurological deficits post-ablation compared to pre-ablation will be summarized descriptively by timepoint.
- **Cerebral Emboli:** The frequency, anatomical location (side and area), and size (diameter and volume) of asymptomatic and symptomatic cerebral emboli observed pre-ablation and new emboli observed post-ablation as determined by MRI evaluations by the core lab will be summarized descriptively by timepoint.
- **Mini Mental State Examination (MMSE):** MMSE scores pre-ablation and change from pre-ablation at the 1-month follow-up will be summarized descriptively and plotted by timepoint.
- **National Institute of Health Stroke Scale (NIHSS):** NIHSS scores pre-ablation and post-ablation prior to discharge will be summarized descriptively and plotted by timepoint.
- **Modified Rankin Scale (mRS):** mRS scores pre-ablation and change from pre-ablation at the 1-month follow-up will be summarized descriptively and plotted by timepoint.

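### The MRI cerebral-emboli result is restricted to subjects with completed neurological assessments, a condition that lesion detection does not need and that neither document defines

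*SAP*

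**What the plan says.** - SAP 7.12.2 lists five items: neurological examination, cerebral emboli, MMSE, NIHSS and mRS. One instruction covers them all: "The analysis will be performed in the Neurological Analysis Set". The emboli item rests on imaging: "new emboli observed post-ablation as determined by MRI evaluations by the core lab will be summarized descriptively by timepoint".
- SAP 5 defines that set as NA-subset subjects who meet the subset's extra eligibility criteria and "have had pre- and post-index-ablation procedure MRI and neurological assessments completed". Protocol 19.3 sets the same joint condition: "The NA analysis set will include 30 subjects who have had pre-and post-index-ablation procedure MRI and neurological assessments completed".
- Both documents give one exception. SAP 5: "Subjects who do not have a pre-index ablation procedure MRI assessment but have no lesions observed on post-procedure MRI assessment will still be included". Protocol 19.3: "Subjects with no pre-index ablation procedure MRI assessment and no lesions observed on post-MRI assessment will be included for analysis". Neither waives a missing neurological assessment.
- Protocol Table 1, footnote 12, repeated in sections 7.2.1, 13.2.1, 13.3.6 and 13.5.2, says: "Patient questionnaires will only be used in countries with validated languages". In the neurological block of the schedule the footnote sits on the row "NIH Stroke Scale ¹²" and on the MMSE row. The neurological examination carries footnote 17 (a qualified physician must perform it), and mRS carries neither.
- Protocol 7.2.1 places 30 subjects in the NA subset.

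**The concern.** Finding a lesion takes an MRI before and an MRI after ablation. The analysis set adds a second condition, so a missing bedside assessment can remove an MRI pair that the core lab could read, including one with new lesions. The NA subset is the only planned systematic cerebral imaging in the trial. Protocol 5.4.1 says that microbubble formation leaves the embolic risk of pulsed field energy unknown, and it cites published pulsed-field rates of 3% to 40%. With 30 subjects there is little imaging to spare.

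The one exception in the definition raises a separate question. It depends on the outcome: a subject with no baseline MRI stays in if the later scan is clean and goes out if it shows a lesion.

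**Working it through.** **1. Which rule governs the denominator.** SAP 7.1.1 bases percentages on non-missing observations. That works within an analysis set. The NA set is applied first, so a subject outside it never reaches the 7.1.1 rule.

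**2. Comparison with the other subsets.** SAP 5 defines the EE set by a readable endoscopy, the CT/MRA set by readable images at both visits, and the PVI durability set by mapping at both procedures. None of these makes an endpoint wait on a different kind of assessment. The NA set does.

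**3. What has to be complete.** The documents support more than one reading.

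| Reading | Support | Consequence for the emboli result |
|---|---|---|
| Neurological examination only | Protocol 7.2.1 names general neurological assessments apart from the scales; 13.2.1 and 13.3.6 also separate examination from scales | No loss through language; only a missed examination excludes |
| Examination plus NIHSS | NIHSS is scheduled before and after ablation | The language limit can exclude |
| Examination plus NIHSS, mRS and MMSE | Protocol 13.2.1 describes the NA work-up this way | The language limit can exclude. Table 1 has no pre-discharge cell for mRS or MMSE and first repeats them at 1 month, so a missed 1-month visit could exclude an MRI pair completed within 72 to 96 hours of ablation |

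Two programmers could therefore produce different denominators from the same data.

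**4. Size.** The plan states no emboli rate or precision for this subset, and 30 is given without derivation, so there is no figure to reproduce. One subject is 1/30 = 3.3% of the subset. The losses and lesion counts below are assumptions, with exact (Clopper-Pearson) 95% intervals.

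Precision, if loss is unrelated to lesions:

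| Observed rate | n = 30 | n = 20 |
|---|---|---|
| 20% | 6/30: 7.7% to 38.6% | 4/20: 5.7% to 43.7% |
| 40% | 12/30: 22.7% to 59.4% | 8/20: 19.1% to 63.9% |

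If no lesion is seen, the upper limit is 1 − 0.025^(1/n): 11.6% at n = 30, 13.7% at n = 25 and 16.8% at n = 20.

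Arithmetic bounds, if x of 30 have lesions and k are dropped: the rate runs from max(0, x − k)/(30 − k), when the dropped subjects have lesions, to x/(30 − k), when none of them has.

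- x = 4, or 13.3% (3.8% to 30.7%). With k = 3: 1/27 = 3.7% to 4/27 = 14.8%. With k = 6: 0/24 = 0% to 4/24 = 16.7%.
- x = 12, or 40.0%. With k = 6: 6/24 = 25.0% to 12/24 = 50.0%.

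These are limits, not forecasts.

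**5. The baseline-MRI waiver.** Let m of 30 subjects lack a pre-procedure MRI, and let every subject have lesion probability p on the post-procedure scan. The m subjects stay only if lesion-free, so the expected rate is about p(30 − m) / [(30 − m) + m(1 − p)].

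| m (assumed) | p = 15% | p = 40% |
|---|---|---|
| 2 | 4.2/29.7 = 14.1% | 11.2/29.2 = 38.4% |
| 4 | 3.9/29.4 = 13.3% | 10.4/28.4 = 36.6% |
| 6 | 3.6/29.1 = 12.4% | 9.6/27.6 = 34.8% |

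Under these assumptions the shift is always downward. The values of p are the top of the consensus range (2% to 15%) and the top of the pulsed-field range in protocol 5.4.1.

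**The case against.** **The endpoint needs more than MRI.** SAP 7.12.2 reports asymptomatic and symptomatic emboli, and protocol 7.2.1 leaves the presence of symptoms to the site neurologist. This stands for classification: without an assessment a lesion cannot be called silent or symptomatic. It does not stand for frequency, location and size, which come from the images.

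**The waiver has a logic.** A clean post-procedure scan shows no new lesion whatever the baseline looked like, whereas a lesion without a baseline cannot be dated. This is true of the individual subject. It does not remove the selection when both kinds of subject should feed one rate.

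**The denominator is 30.** Protocol 19.3 describes 30 completers. But 7.2.1 includes 30 subjects, SAP 5 gives no number, and the replacement rule in protocol 9.2 covers only subjects found ineligible before catheter insertion. A later gap in assessments has no stated replacement.

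**A reader might infer that language limits are certain to remove subjects, or that they bias the emboli rate.** The documents support neither. The limit touches NIHSS and MMSE only, and it matters only if those scales count toward completion. No site in the subset is said to lack a validated language, and no link between language and lesions is shown.

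**A reader might also infer that a full MRI pair is always required, or that clinical strokes could go uncounted.** The waiver contradicts the first. As to the second, stroke and TIA are primary adverse events, analysed in the mITT set with the SP set as sensitivity analysis, and do not depend on the NA set.

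**Conclusion.** The point holds as a minor one. As written, the plan leaves a subject with readable MRI before and after ablation but an incomplete neurological assessment out of the MRI emboli result, and it does not say what complete means. How many subjects this affects cannot be known from the documents and may be none. Loss driven by language alone would widen the interval rather than clearly bias the rate; the wider bounds in the working apply only if loss is related to lesions, which is not shown. The waiver is the more directional feature: it lowers the expected rate by about 0.9 to 5.2 percentage points over the assumed cases (15.0 − 14.1 and 40.0 − 34.8), provided lesion risk does not depend on having a baseline scan. The NA endpoints are descriptive and carry no hypothesis test, so study success is not affected.

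**What to change.** In SAP 5 and 7.12.2, define the denominator by endpoint:

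1. Summarise emboli frequency, location and size in all NA-subset subjects with readable pre- and post-ablation MRI, whatever their neurological assessments.
2. Report a lesion with no symptom assessment as unclassified, beside asymptomatic and symptomatic.
3. Show subjects admitted under the missing-baseline waiver on a separate line, together with those lacking a baseline MRI who had post-procedure lesions, so that both sides of the exception are visible.
4. Analyse the neurological examination, NIHSS, mRS and MMSE each in subjects with that measure at baseline and at the relevant timepoint, and print every denominator.

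This removes the need for a single definition of completed assessments. If a joint set is kept for any other summary, name its instruments and timepoints. Protocol 19.3 has the same definition, so align it or record the departure in the SAP. The cost is wording and a few extra table rows, with no new data collection; denominators will differ between rows.

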#### **7.12.3 Analysis of CT/MRA Endpoint**

Incidence of PV stenosis in the CT/MRA subset up to 3 months post-ablation will be summarized with the number and percentage of subjects and vein level with PV stenosis as defined by the core lab. The analysis will be performed in the Cardiac CT/MRA Analyses Set.

#### **7.12.4 Analysis of EE Endpoint**

The number and percentage of subjects experiencing esophageal thermal lesions in the region of the contact area between the esophagus and LA as determined by post-procedure endoscopy and assessed by the core lab will be summarized. The analysis will be performed in the EE Analyses Set.

## **8. Data Monitoring Committee (DMC)**

Data Monitoring Committee (DMC) will assess subjects' data for safety on frequent intervals and make recommendations on study adaptations as described in the DMC Charter.

